APPENDIX D. NEW YORK HEART ASSOCIATION CLASSIFICATIONS

1994 Revisions to Classification of Functional Capacity and Objective Assessment of Patients with Diseases of the Heart

Functional Capacity	Objective Assessment
Class I. Patients with cardiac disease but without resulting limitation of physical activity. Ordinary physical activity does not cause undue fatigue, palpitation, dyspnea, or anginal pain.	A. No objective evidence of cardiovascular disease.
Class II. Patients with cardiac disease resulting in slight limitation of physical activity. They are comfortable at rest. Ordinary physical activity results in fatigue, palpitation, dyspnea, or anginal pain.	B. Objective evidence of minimal cardiovascular disease.
Class III. Patients with cardiac disease resulting in marked limitation of physical activity. They are comfortable at rest. Less than ordinary activity causes fatigue, palpitation, dyspnea, or anginal pain.	C. Objective evidence of moderately severe cardiovascular disease.
Class IV. Patients with cardiac disease resulting in inability to carry on any physical activity without discomfort. Symptoms of heart failure or the anginal syndrome may be present even at rest. If any physical activity is undertaken, discomfort is increased.	D. Objective evidence of severe cardiovascular disease.

APPENDIX E. IMMUNE-RESPONSE RELATED CRITERIA

Immune-response related criteria (irRC) based on bidimensional measurements of measurable lesions were first introduced by Wolchok et al in 2009. This protocol will adopt a modified version of the criteria based on unidimensional measurements of measurable lesions, as described by Nishino et al in 2013 and 2014, as follows:

At the baseline tumor assessment, the sum of the longest diameters (SLD) of all identified index lesions (2 per organ, up to 5 in total) will be calculated. At each subsequent tumor assessment, the SLD of the index lesions and of new measurable lesions (2 per organ, up to 5 in total) are added together to provide the total tumor burden = $SLD_{index\ lesions} + SLD_{new,\ measurable\ lesions}$. Total tumor burden will be used to assess the immune related response as described in the table below.

Immune-Response Related Criteria	
Index Lesions (Baseline	Up to 2 per organ, up to 5 in total
Measurable Lesions)	(see RECIST 1.1 for guidelines on measurable lesions)
	• ≥10 mm in the longest diameter for all except for lymph nodes
	• ≥15 mm in short axis for lymph nodes
New Lesions (Measurable)	Up to 2 per organ, up to 5 in total
	• ≥10 mm in the longest diameter for all except for lymph nodes
	• ≥15 mm in short axis for lymph nodes
Tumor Burden	SLD _{index lesions} + SLD _{new, measurable lesions}
	If a lymph node qualifies and chosen as a new measurable lesion for
	tumor burden calculations, its short axis length is included in the sum
	(SLD _{new, measurable lesions})
Immune Related Response	PD: ≥20% increase in tumor burden from nadir
Assessment	PR: ≥30% decrease in tumor burden from baseline
	SD: Neither sufficient shrinkage to qualify for PR nor sufficient increase
	to qualify for PD
	CR: Disappearance of all lesions including non-index lesions and new
	non-measurable lesions, lymph nodes must be <10 mm in short axis)
Confirmation	Confirmation is required for CR, PR and PD by a consecutive
	observation not less than 4 weeks apart

Source: Wolchok 2009; Nishino 2013; Nishino 2014.

## **VERSION HISTORY**

Version	Date	Description
1.0	19 April 2019	Original final version

## LIST OF ABBREVIATIONS

AE	adverse event
ALT	alanine transferase
ANC	absolute neutrophil count
AST	aspartate aminotransferase
AUC	area-under-the-concentration time curve
BUN	blood urea nitrogen
CIV	central imaging vendor
C max	maximum observed concentration
C min	minimum observed concentration
CR	complete response
CRF	case report form
СТ	computed tomography
CTCAE	Common Terminology Criteria for Adverse Events
DCE-MRI	dynamic contrast-enhanced magnetic resonance imaging
DCR	disease control rate
DLT	dose limiting toxicity
DOR	duration of response
ECG	electrocardiogram
ECOG	Eastern Cooperative Oncology Group
НА	Hyaluronan
HA-high	hyaluronan high
irRC	immune-related response criteria
INR	international normalized ratio

MedDRA	Medical Dictionary of Regulatory Activities
MRI	Magnetic Resonance Imaging
MTD	maximum tolerated dose
NSCLC	non-small cell lung cancer
ORR	objective response rate
OS	overall survival
PD	Pharmacodynamics
PD-1	Programmed cell death-1
PD-L1	Programmed death-ligand 1
PEGPEM	PEGylated recombinant human hyaluronidase combined with pembrolizumab
PEGPH20	PEGylated recombinant human hyaluronidase
PET	positron emission tomography
PFS	progression free survival
РК	Pharmacokinetics
PR	partial response
РТ	prothrombin time
PTT	partial prothrombin time
RECIST	response evaluation criteria in solid tumors
RP2D	recommended phase 2 dose
SAE	serious adverse event
SAP	statistical analysis plan
T 1/2	terminal half-life
ТВ	total bilirubin

TEAE	treatment emergent adverse event
T max	time to maximum concentration
TME	tumor microenvironment
ULN	upper limit of normal

## 1 INTRODUCTION

The purpose of this document is to provide a description of the statistical methods and procedures to be implemented in the analysis of data collected in the study HALO-107-101 conducted by Halozyme, Inc. This document is based on the Protocol HALO-107-101 Amendment 4 entitled "A Phase 1b Open-Label Study of PEGylated Recombinant Human Hyaluronidase (PEGPH20) Combined with Pembrolizumab in Subjects with Selected Hyaluronan-High Solid Tumors" and dated 6 November 2017.

## **2** STUDY OBJECTIVES

The study has two portions, namely, a Dose Escalation portion and a Dose Expansion portion. The objectives for each portion are as follows.

## 2.1 Dose Escalation

**Primary**:

- To assess the safety and tolerability of PEGylated recombinant human hyaluronidase (PEGPH20) combined with pembrolizumab (Keytruda®) (PEGPEM) in subjects with relapsed/refractory non-small cell lung cancer (NSCLC) and relapsed/refractory gastric adenocarcinoma.
- To determine the recommended phase 2 dose (RP2D) of PEGPH20 when administered with pembrolizumab in subjects with relapsed/refractory NSCLC or relapsed/refractory gastric adenocarcinoma.

#### Secondary:

- To assess the pharmacokinetics (PK) of PEGPH20 when given in combination with pembrolizumab in subjects with relapsed/refractory NSCLC or relapsed/refractory gastric adenocarcinoma.
- To obtain an early assessment of the antitumor activity of PEGPEM, as assessed by objective response rate (ORR), duration of response (DOR), disease control rate (DCR) and progression free survival (PFS) based on Response Evaluation Criteria in Solid Tumors (RECIST) v1.1, and overall survival (OS) in subjects with relapsed/refractory NSCLC or relapsed/refractory gastric adenocarcinoma.

#### Exploratory:

• To assess the PK of pembrolizumab when given in combination with PEGPH20 in subjects with relapsed/refractory NSCLC or relapsed/refractory gastric adenocarcinoma.

## 2.2 Dose Expansion

The objectives described below will be evaluated in hyaluronan-high (HA-high) subjects with relapsed/refractory NSCLC and HA-high subjects with relapsed/refractory gastric adenocarcinoma.

Statistical Analysis Plan Version Number: 1.0

#### **Primary**:

• To evaluate the efficacy of PEGPEM as assessed by ORR based on RECIST v1.1.

#### Secondary:

- To evaluate the efficacy of PEGPEM as assessed by DOR, DCR, and PFS based on RECIST v1.1, and OS.
- To evaluate the efficacy of PEGPEM as assessed by ORR, DOR, DCR, and PFS based on immune-related response criteria (irRC).
- To characterize the PK of PEGPH20 when given in combination with pembrolizumab.
- To evaluate the safety and tolerability profile of PEGPEM.

#### Exploratory:

- To evaluate the efficacy of PEGPEM, as assessed by ORR, DOR, DCR and PFS based on RECISIT v1.1 criteria and irRC, by programmed death-ligand 1 (PD-L1) expression levels.
- To assess the treatment effect of PEGPEM as follows:
  - Based on HA levels in plasma and tumors, or other potential biomarkers.
  - Based on tumor blood flow and metabolic activity as assessed by dynamic contrastenhanced magnetic resonance imaging (DCE-MRI) and positron emission tomography (PET)/computed tomography (CT) scans, respectively.
- To assess the PK of pembrolizumab when given in combination with PEGPH20.

## **3 STUDY OVERVIEW**

## 3.1 Study Design

This Phase 1b study of PEGPEM consists of 2 portions:

- A Dose Escalation portion in subjects with relapsed/refractory Stage IIIB or IV NSCLC after failing at least 1 previous platinum-based chemotherapy regimen (refer to Inclusion Criterion #2 in the protocol) and subjects with relapsed/refractory locally advanced or metastatic gastric adenocarcinoma after failing at least 1 previous chemotherapy regimen for locally advanced or metastatic disease.
- Followed by a Dose Expansion portion in:
  - Previously untreated, hyaluronan-high (HA-high) subjects with Stage IIIB or IV NSCLC
  - Previously treated, HA-high subjects with relapsed/refractory Stage IIIB or IV NSCLC having failed no more than 1 previous platinum-based chemotherapy regimen (refer to Inclusion Criterion #3 in the protocol) for locally advanced or metastatic disease

 HA-high subjects with relapsed/refractory locally advanced or metastatic gastric adenocarcinoma having failed no more than 2 previous chemotherapy regimens for locally advanced or metastatic disease

Since PEGPH20 has not been evaluated in clinical studies in combination with pembrolizumab, this study will have a Dose Escalation portion to evaluate the safety and tolerability of PEGPEM treatment before the Dose Expansion portion is initiated. The Dose Escalation portion will also be used to determine the dose of PEGPH20 to be evaluated in the Dose Expansion portion.

#### **3.1.1 Phase 1b Dose Escalation Portion**

This portion of the study is a single-arm, dose escalation study of PEGPH20 in combination with pembrolizumab. Using a standard 3+3 dose escalation design, approximately 3 to 6 subjects in each cohort will receive PEGPH20 + pembrolizumab. PEGPH20 will be administered on Day 1, Day 8 and Day 15 of each 21-day cycle to consecutive cohorts in increasing dose levels (1.6, 2.2, 2.6, 3.0, and 4.0 µg/kg). Pembrolizumab will be administered on Day 1 of each cycle, 4-6 hours after the dose of PEGPH20. If the maximum tolerated dose (MTD) is not reached at 4.0 µg/kg, higher doses may be evaluated. If  $\geq$ 2 subjects experience a dose limiting toxicity (DLT) at the 1.6 µg/kg dose level, Cohort -1 will be opened and subjects will be dosed at 1.0 µg/kg on Day 1, Day 8, and Day 15 of each 21-day cycle. The RP2D of PEGPH20 will be the MTD determined in Dose Escalation or the Sponsor may decide to choose a dose lower than the MTD and which has completed evaluation in Dose Escalation and is found to be safe and tolerable to evaluate in Dose Expansion.

The number of cohorts studied and number of subjects exposed to a given dose level will depend on the doses tested. It is anticipated that up to 5 dose levels will be studied for a total of approximately 30 subjects exposed to study medication. The dose allocation for 5 cohorts of subjects assigned to the 5 preselected dose levels and the -1 cohort assigned to the preselected dose of 1.0  $\mu$ g/kg (if  $\geq$ 2 subjects experience a DLT at 1.6  $\mu$ g/kg dose level) is shown as an example in Table 1. Study medication dosing and treatment schedule is shown in Table 2.

Cohort	PEGPH20 µg/kg	Pembrolizumab mg/kg
-1	1.0	2
1	1.6	2
2	2.2	2
3	2.6	2
4	3.0	2
5	4.0 a	2

Table 1:	Dose Allocation and Cohort Schedule - Dose Escalation Portion

Abbreviations: PEGPH20 = PEGylated Recombinant Human Hyaluronidase

Note: Each treatment cycle is 21 days. Dose interruption and modifications are permitted.

a If the MTD is not reached at 4.0  $\mu$ g/kg, higher doses may be evaluated.

Safety data from all subjects dosed will be reviewed to determine the RP2D. Dose escalation will be guided by safety data from each subject during the 21 days following their first dose of

PEGPH20. Intra-subject dose escalation to the next PEGPH20 dose studied may be allowed if the Investigator deems it in the best interest of the subject and after discussion with the Sponsor and provided the next PEGPH20 dose studied has been determined not to have exceeded the MTD.

- If none of initial 3 subjects in a given cohort experience a DLT within 21 days of starting treatment, enrollment and dosing may proceed at the next planned dose level.
- If 1 of 3 initial subjects at a given dose level experiences a DLT within the first 21 days of treatment, 3 additional subjects will be enrolled and dosed at the same dose level. If ≤1 of 6 subjects experiences a DLT, dose escalation may continue to the next planned higher dose.
- If ≥2 subjects at a given dose level experience a DLT within the first 21 days of treatment, that dose level will be considered to have exceeded the MTD and dose escalation will be stopped. If the previous dose level did not already have 6 subjects treated with ≤1 DLT, enrollment and dosing will then resume in the previous dose level with additional subjects up to a total of 6 subjects. The highest dose level at which no more than 1 of 6 evaluable subjects has experienced a DLT in the first 3 weeks of treatment will be considered the MTD for the PEGPEM combination. The RP2D will be based on the overall safety profile.
- If  $\geq 2$  subjects at the 1.6 µg/kg dose level experience a DLT within the first 21 days of treatment, Cohort -1 will be opened at a lower dose level of 1.0 µg/kg.

**Note**: Additional subjects may be enrolled in each cohort to further assess the tolerability of PEGPEM and determine an acceptable safety profile prior to the enrollment in the next dose level and Dose Expansion portion of the study.

#### 3.1.2 Phase 1b Dose Expansion Portion

Approximately 51 HA-high subjects will be studied in the Dose Expansion portion at the RP2D identified in the Dose Escalation portion:

- Approximately 30 subjects with Stage IIIB or IV NSCLC, previously untreated or treated and having failed no more than 1 previous platinum-based chemotherapy (refer to Inclusion Criterion #3)
- Approximately 21 subjects with relapsed/refractory gastric adenocarcinoma having failed no more than 2 previous chemotherapy regimens.

In Dose Expansion, PEGPH20 will be administered on Day 1, Day 8, and Day 15 of each 21-day cycle (i.e., 3 doses / cycle) and pembrolizumab (200 mg every 21 days) on Day 1 of each cycle (i.e., 1 dose / cycle), 4-6 hours after the completion of PEGPH20 administration. The dosing schedule is shown in Table 2.

If a dose of PEGPH20 is missed on Day 1 of Cycle 2 or beyond, the cycle will continue as scheduled. If it is known that pembrolizumab will be missed or held on Day 1, PEGPH20 should also be held and the cycle will not start until the first dose of pembrolizumab is administered. This will require planning such that the dose of PEGPH20 can be given before the pembrolizumab dose is set to resume.

Time point	PEGPEM Treatment by Treatment Group		
Subjects with NSCLC			
Cycle 1 and B	eyond (Each Cycle 21 Days)		
Week 1			
Day 1	PEGPH20		
	Pembrolizumab (4-6 hours after PEGPH20)		
Week 2			
Day 8	PEGPH20		
Week 3			
Day 15	PEGPH20		
Subjects with Gastric Adenocarcinoma			
Cycle 1 and B	eyond (Each Cycle 21 Days)		
Week 1			
Day 1	PEGPH20		
	Pembrolizumab (4-6 hours after PEGPH20)		
Week 2			
Day 8	PEGPH20		
Week 3			
Day 15	PEGPH20		

# Table 2:Study Medication Dosing and Treatment Schedule – Dose Escalation and
Dose Expansion

Abbreviations: PEGPEM = PEGPH20 in combination with pembrolizumab; PEGPH20 = PEGylated Recombinant Human Hyaluronidase; NSCLC = non-small cell lung cancer

Notes: Dose interruption and modifications are permitted.

Subjects with NSCLC will be studied first, followed by subjects with gastric adenocarcinoma.

Visit window is  $\pm 2$  days of the specified times.

## **3.2 Discontinuation of Treatment**

Treatment in both portions of the study will continue until death, withdrawal of consent from the study, disease progression, or unacceptable toxicity; however, subjects with asymptomatic disease progression will be allowed to continue study treatment at the Investigator's discretion despite evidence of increasing tumor burden or appearance of new lesions for up to 6 weeks if the subject is "clinically stable". Clinically stable is defined as:

- Absence of symptoms and signs indicating clinically significant PD (including worsening of laboratory values) indicating disease progression and
- No decline in Eastern Cooperative Oncology Group (ECOG) performance status and
- Absence of rapid progression of disease or of progressive tumor at critical anatomical sites (e.g., cord compression) requiring urgent alternative medical intervention.

Dose interruptions and modifications of study treatment are permitted. Investigators may also discontinue study treatment if it is no longer in the best interest of the subject.

## 3.3 Study Centers

Both portions of the study will be conducted at multiple centers.

## 3.4 Randomization and Blinding

This is a multi-center, open-label, non-randomized study.

## 3.5 Study Duration

The study will consist of an optional prescreening period for HA-testing in Dose Expansion (per Protocol Amendment 4), a screening period of up to 28 days, a treatment period (21-day cycles), a 30-day post-treatment period (after last dose) for collection of AEs and a long-term follow-up. Subjects who discontinue treatment with PEGPH20 and pembrolizumab will be followed every 12 weeks for survival until death, withdrawal of consent, or lost to follow-up.

## 3.6 Tumor Response and Disease Progression Assessment

In both portions of the study, tumor response and progression will be assessed by the Investigator at the end of Cycle 2, Cycle 4 and then at the end of every fourth treatment cycle thereafter (i.e., Week 3 of Cycles 2, 4, 8, 12, 16 and beyond) based on RECIST v1.1 criteria (Eisenhauer 2009; see Appendix C of the protocol). In the dose expansion portion, tumor response and progression will also be assessed by the Investigator at the end of above mentioned cycles using a modified unidimensional version of the irRC criteria (Nishino 2013, Nishino 2014; see Appendix E of the protocol) first introduced by Wolchok (2009). Tumor assessment scans (CT/MRI of chest, abdomen, pelvis, and other areas of known or newly suspected disease) should be performed at Screening (within 28 days prior to first dose of study drugs) and obtained any time on or after Day 15 (of Cycles 2, 4, 8, 12, 16 and every fourth treatment cycle thereafter) to allow enough time for the scan to be reviewed locally prior to the subject's next scheduled dosing visit.

Additionally, tumor images associated with NSCLC cancer type will be assessed by an independent reviewer from a third-party vendor, Imaging Endpoints. Efficacy analyses related to NSCLC cancer type using RECIST v1.1 will also be performed based on the tumor assessments from Imaging Endpoints.

A CT/MRI brain scan must be performed at Screening (within 28 days prior to first dose of study drugs), to assess potential central nervous system disease and/or metastases.

For the duration of the study (i.e., post-baseline), CT/MRI of the brain will be performed if clinically indicated, and within a target of 1 week after a subject achieves a complete response (CR). For NSCLC subjects with a history of treated brain metastases, brain scans will be performed at tumor assessment time points.

For a confirmed best response of CR or partial response (PR) based on RECIST v1.1 and irRC, a confirmatory scan must be performed no sooner than 28 days after the initial scan that showed a PR or a CR. A confirmatory scan should also be performed to confirm disease progression (PD) based on irRC no sooner than 28 days after the initial scan that showed progression.

## **3.7 Disease Progression Criteria**

Disease progression will be defined by the presence of 1 or both of the following, based on the Investigator's assessment:

- Disease progression documented by CT scan/MRI scan based on RECIST v1.1.
- Clinical tumor-related progression that is well documented in the absence of scans demonstrating radiographic disease progression.

## 4 STATISTICAL METHODS

#### 4.1 General Considerations

In general, continuous variables will be summarized using descriptive statistics (N, mean, standard deviation [SD], median, minimum [min], maximum [max], and quartiles). Categorical variables will be summarized using frequencies and percentages. In each summary table, figure or data listing, analysis population considered will be included in the title.

PEGPH20 and pembrolizumab are referred to as study drugs.

Study day 1 for a subject is defined as the first day that any study treatment is administered to the subject. The day before the study day 1 is referred to as study day -1. Unless otherwise indicated, the baseline value of a parameter is defined as the latest non-missing value taken prior to the administration of any study drug.

Statistical analyses will be performed and related outputs will be produced using the SAS® software Version 9.3 or higher. All tables, figures, and data listings will be independently checked for accuracy, consistency, and integrity in accordance with Medpace standard operating procedures or work instructions.

## 4.2 Missing Data

Time to event parameters will be censored for all subjects who do not experience the event of interest (progressive disease or death). In ORR analysis, subjects with no tumor response assessment will be treated as non-responders.

All available efficacy and safety data will be included in data listings and tabulations. In general, missing data will be treated as missing and no data imputation will be applied, unless otherwise specified. Missing dates will be presented without any imputation in all data listings.

#### Missing/Partial Dates in Adverse Events

AE stop dates that are partially missing will be imputed as follows:

- If month and year are present but day is missing, the last day of the month will be used to impute the missing day.
- If only year is present but day and month are missing, the 31DEC will be will be used to impute the missing day and month.

After the imputation, the imputed dates will be compared against the date of death, if available. If the date is later than the date of death, the date of death will be used instead.

If the AE stop date is completely missing, it will remain missing.

AE start dates that are partially missing will be imputed as follows:

- If month and year are present but day is missing, the first day of the month will be used to impute the missing day unless the month and year are the same as month and year of first dose date. In that case, day of first dose date will be used to impute the missing day.
- If only year is present but day and month are missing, first dose date will be used to impute if the year is same as the year of first dose date, otherwise 01JAN will be used to impute the missing day and month.

If the imputed date is later than the stop date, then the stop date will be used instead.

If AE start date is completely missing, then the first dose date will be used.

#### **Missing/Partial Dates of Concomitant Medication**

Concomitant medications with start dates that are partially missing will be analyzed as follows:

- If the start date has month and year but day is missing, the medication will be included in the summary table if the month and year of the start date of the event are
  - on or after the month and year of the date of the first dose of study medication AND
  - on or before the month and year of the date of the last dose of study medication plus 30 days.
- If the start date has year, but day and month are missing, the medication will be included in the summary table if the year of the start date of the event is
  - on or after the year of the date of the first dose of study medication AND
  - $\circ$  on or before the year of the date of the last dose of study medication plus 30 days.

If the start date of a therapy is completely missing, then the therapy will be included in the summary table unless a partial or complete end date is before the first dose date.

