#### 4.6.4 Prior and Concomitant Medications

Prior medications are those the subject used prior to the first dose date. Prior medications can be discontinued before first dosing or can be ongoing during treatment phase.

Concomitant medications are defined as medications that were either initiated prior to the first dose of study drug and continued during the study treatment, or initiated on or after the date of the first dose of study drug till the end of the last dose of study drug plus 30 days. A given medication can be classified both as a prior medication and as a concomitant medication depending on the start and stop dates.

A summary showing the number and percentage of subjects who took either prior and/or concomitant medications will be coded by WHO therapeutic drug class, and summarized separately by anatomic therapeutic class (ATC) and preferred term using frequencies and percentages for subjects in the Safety Population by cancer type and in total. In these summaries, subjects taking more than one medication in the same ATC or preferred name will be counted only once under that ATC or preferred term. All prior and concomitant medications will also be listed.

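### The SAP's partial-date rule for concomitant medications contradicts its own definition: it can omit earlier-started drugs still in use and admit some that stopped before first dose

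*SAP*

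**What the plan says.** SAP 4.6.4 defines concomitant medications in two limbs. The first covers "medications that were either initiated prior to the first dose of study drug and continued during the study treatment". The second covers those "initiated on or after the date of the first dose of study drug till the end of the last dose of study drug plus 30"; the unit is days. The section adds: "A given medication can be classified both as a prior medication and as a concomitant medication depending on the start and stop dates".

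SAP 4.2, under the heading on missing or partial concomitant medication dates, says how concomitant medications "with start dates that are partially missing will be analyzed as follows":

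- **Day missing:** tabulated if the start month and year are "on or after the month and year of the date of the first dose of study medication AND" no later than the month and year of last dose plus 30 days.
- **Day and month missing:** tabulated if the start year is "on or after the year of the date of the first dose of study medication AND" no later than the year of last dose plus 30 days.
- **No start date at all:** "then the therapy will be included in the summary table unless a partial or complete end date is before the first dose date".

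The end date or ongoing status is consulted only in the third case.

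**The concern.** The two partial-date branches carry only the second limb of the definition. Neither has a path for a drug that began before first dose and was still being taken, which is the first limb. Long-standing medications are a natural place to find partial start dates, since a subject may recall the year but not the day.

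The rule also behaves oddly across degrees of missingness: knowing that a drug began in an earlier year can remove it from the table, while knowing nothing about its start keeps it.

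At stake is whether the concomitant medication table describes what subjects were taking during treatment. Co-medication is relevant background here. The protocol (10.12) asks sites to record other anticoagulants and permits analgesics and muscle relaxants for musculoskeletal events, and SAP 4.9.4 tabulates thromboembolic, bleeding and musculoskeletal events.

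**Working it through.** The plan gives no figure to reproduce, and no sample size, power or event count is involved. The check applies the SAP 4.2 rule and the SAP 4.6.4 definition to the same test records.

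**Inputs.** The rule and definition are as quoted above. The dates are illustrative and do not come from the documents: first dose 15 Jun 2017, last dose 10 Dec 2017. The window therefore closes on 10 Dec 2017 + 30 days = 9 Jan 2018.

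**Tests.**
- SAP 4.2, day missing: Jun 2017 ≤ start month and year ≤ Jan 2018.
- SAP 4.2, year only: 2017 ≤ start year ≤ 2018.
- SAP 4.6.4: started before first dose and continued during treatment, or started from first dose to 9 Jan 2018.

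| Recorded start | Status | SAP 4.2 rule | SAP 4.6.4 definition |
|---|---|---|---|
| 10 Mar 2012 | ongoing | does not apply (complete date) | concomitant |
| Mar 2012 | ongoing | not met (Mar 2012 < Jun 2017) | concomitant |
| 2012 | ongoing | not met (2012 < 2017) | concomitant |
| May 2017 | ongoing | not met (May 2017 < Jun 2017) | concomitant |
| Jun 2017 | ongoing | met | concomitant |
| 2017 | ongoing | met | concomitant |
| none | ongoing | included | cannot be excluded |
| 2017 | stopped 1 Mar 2017 | met | not concomitant |
| Jun 2017 | stopped 10 Jun 2017 | met | not concomitant |

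**Omission.** In rows 2 to 4 the rule fails drugs that the definition counts. The same drug with a complete 2012 date (row 1) is concomitant, and with no start date (row 7) it is tabulated. Only the intermediate state of knowledge drops it. A drug started in 2012 and stopped after first dose, during treatment, would fail in the same way.

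**Over-inclusion.** In rows 8 and 9 the start falls in the first-dose year or month, so the rule is met, although the drug stopped before 15 Jun 2017.

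**Where the rule is harmless.** Rows 5 and 6 agree: partial starts within the first-dose month or year are kept if the drug is ongoing.

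**After the fix.** In rows 2 to 4 the earliest possible starts are 1 Mar 2012, 1 Jan 2012 and 1 May 2017. All are before 9 Jan 2018 and the drugs are ongoing, so they are counted. In rows 8 and 9 the stop dates precede 15 Jun 2017, so they are not counted. Rows 5 and 6 do not change.

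**The case against.** The strongest defence is that SAP 4.2 says *if*, not *only if*. The passage concerns drugs already labelled concomitant, and SAP 4.2 also says generally that all available safety data go into listings and tabulations. On this reading the branches settle only ambiguous starts, and SAP 4.6.4 still admits earlier starts that continued. The reading is possible, but the SAP does not state it. The branches are the only inclusion test given for partial start dates, so a programmer following them literally would omit the records. The changes listed in SAP section 5 do not address the point.

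Other objections limit the consequences, and they stand:

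- An omitted drug is not lost. It still meets the SAP 4.6.4 description of a prior medication, and all prior and concomitant medications are listed. SAP 4.6.4 leaves unclear whether the two are tabulated together; if they are, the omission may not show.
- Subjects are counted once per ATC class or preferred term. One leaves a row only if no other qualifying drug falls there.
- Protocol-mandated aspirin and enoxaparin are scheduled from Cycle 1 Day 1, so those courses start inside the window.

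A reader might infer that whatever share of baseline medications has partial start dates vanishes from the table. The documents give no such share. Even an assumed one would overstate the loss, because starts in the first-dose month or year are kept. A reader might also infer that thromboembolic, bleeding, musculoskeletal or immune-response results are distorted. No planned analysis of these uses the concomitant table: SAP 4.7.5 has no covariate adjustment and SAP 4.8 no subgroup analysis. Chronic steroids would be a poor example, since their use for pain or emesis is an exclusion criterion and protocol 8.4 advises against systemic corticosteroids before pembrolizumab.

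**Conclusion.** The conflict between SAP 4.2 and SAP 4.6.4 is real and visible in the text. Read as the operative test for partial start dates, the rule misclassifies in both directions. It may omit drugs with a partial start before the first-dose month or year that were still in use, and it includes some drugs that stopped before first dose. Calling it simply an undercount would describe only one side.

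The number of subjects affected cannot be computed. It depends on how many start dates are partial, how many of those fall before the first-dose month or year, and whether another drug keeps the subject in the same row. The effect is confined to a descriptive medication table. No efficacy, DLT or adverse-event result changes. This is a minor correction, worth making because the stated rule is wrong rather than merely brief.

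The conclusion rests on reading the branches as the inclusion test for partially dated medications. If the sponsor intended SAP 4.6.4 to override them, the text still needs to say so.

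**What to change.** In SAP 4.2, replace the day-missing and year-only branches with one rule: count a medication with a partial start date as concomitant if its earliest possible start date is on or before last dose plus 30 days, and it is either ongoing or its latest possible stop date is on or after first dose. The branch for a completely missing start date already uses the end date and can stay.

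This covers both limbs of SAP 4.6.4 and removes the over-inclusion of drugs known to have stopped before first dose. Where a partial stop date leaves the matter open, it resolves towards inclusion, in line with the completely missing branch. It would help to state in SAP 4.6.4 whether prior and concomitant medications are tabulated separately.

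The cost is a short change of SAP wording and the matching programming. No new data are needed.
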